10.2 Sample Size and Accrual

MF and AMKL are rare diseases with total prevalence (total number of patients with the disease in the US at any time) under 15,000. NIH considers prevalence under 200,000 a rare disease. A total of 24 subjects (maximum 24 subjects, regardless of the disease breakdown of MF or AMKL. If all 24 were MF, that would be acceptable) will be accrued to this trial. Approximately 4 potentially eligible patients are seen per month at all sites, and it is anticipated that at least 1 per month will be accrued, leading to a 2 year accrual period.

. Approximate standard errors for the estimated response rate when the true response rate is 10% are +/- 6% with a sample of 24 patients total, +/- 18% with a sample of 18 patients, +/- 9% with 12 patients and +/- 10% to 12% with 6 patients. In the event that a patient consents and is registered to the study but never begins treatment, that patient may be replaced. The QAM must be notified and, if necessary, DMC approval must be obtained.

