2.0 OBJECTIVES & ENDPOINTS

2.1 Primary Objective & Endpoint

The primary objective of this pilot study is to determine the safety profile of alisertib in patients with AMKL and in patients with MF.

Adverse events will be defined according to the National Cancer Institute's Common Terminology Criteria for Adverse Events (NCI CTCAE) version 4.0. The number, frequency, and severity of adverse events will be recorded every cycle for each population. All patients who receive at least 1 dose of alisertib will be considered evaluable for this endpoint.

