6.0 ENDPOINT ASSESSMENT

6.1 Primary Endpoint

The primary objective of this pilot study is to determine the safety profile of alisertib in patients with AMKL and in patients with MF.

Adverse events will be defined according to the National Cancer Institute's Common Terminology Criteria for Adverse Events (NCI CTCAE) version 4.0. The number, frequency, and severity of adverse events will be recorded every cycle for each population. All patients who receive at least 1 dose of alisertib will be considered evaluable for this endpoint.

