10.0 STATISTICAL CONSIDERATIONS

10.1 Statistical Analysis

10.1.1 Primary Endpoint

The primary objective of this pilot study is to determine the safety profile. All adverse events (AEs) will be summarized using frequencies and percentages. These percentages will be subclassified by type of AE, timing of AE in the treatment cycle, frequency and attribution of AEs (treatment related or not).

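### The accepted split of 24 MF and 0 AMKL patients can leave the AMKL half of the primary safety objective unanswered, and no precision is stated for any adverse event rate

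*Combined protocol and SAP*

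**What the plan says.** Section 2.1 states the primary aim as to "determine the safety profile of alisertib in patients with AMKL and in patients with MF". The Study Summary and 6.1 repeat it, and 1.6 gives safety and preliminary efficacy in each population as the overall goals. Section 6.1 adds: "The number, frequency, and severity of adverse events will be recorded every cycle for each population". Anyone who takes one dose is evaluable.

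On numbers, 10.2 allows a "maximum 24 subjects, regardless of the disease breakdown of MF or AMKL" and continues: "If all 24 were MF, that would be acceptable". The Study Summary and section 3.0 say the same. No section sets a minimum number of AMKL patients or says what becomes of the AMKL objective if few or none enrol.

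On analysis, 10.1.1 says: "All adverse events (AEs) will be summarized using frequencies and percentages". It then subdivides by type, timing in the cycle, frequency and attribution. Disease is not in that list, and no interval is planned. Section 10.1.2, by contrast, plans an exact binomial 95% interval for response, the secondary endpoint. The one precision statement in 10.2 also concerns response. It opens "Approximate standard errors for the estimated response rate when the true response rate is 10" per cent and gives figures for 24, 18, 12 and 6 patients.

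**The concern.** The objective and the enrolment rule do not fit together. A trial that enrols 24 MF patients has followed the protocol in full and has no AMKL safety data, yet half of its primary objective concerns AMKL.

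MF results cannot fill the gap on the protocol's own reasoning. Section 1.6 justifies the pilot by saying that safety is undocumented in either disease. Entry conditions also differ in ways that bear on toxicity: 3.2.5 requires minimum neutrophil and platelet counts for MF, and 3.1.4 sets none for AMKL.

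The second part concerns what a small AMKL group can show. If a few AMKL patients enrol and a given event does not occur, 10.1.1 as written yields 0% with no bound, possibly pooled with MF. The report would then not show how little a small group excludes, although the secondary endpoint would carry an exact interval in the same report.

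**Working it through.** **Inputs from the documents.** Maximum of 24 patients with any split (10.2); group sizes 24, 18, 12 and 6 (10.2); true response rate 10% (10.2); exact binomial method at 95% (10.1.2). **Assumptions.** No adverse event rate is planned for, so 5%, 10% and 20% are used as an illustrative range.

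**Step 1: the plan's own precision figures.** The standard error of a proportion is √[p(1−p)/n] with p = 0.10.

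| n | √(0.09/n) | Stated in 10.2 |
|---|---|---|
| 24 | 6.1% | 6% |
| 18 | 7.1% | 18% |
| 12 | 8.7% | 9% |
| 6 | 12.2% | 10% to 12% |

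The statement "6% with a sample of 24 patients total" reproduces, and so does the figure for 12. At 6, the upper end of the stated range agrees. The figure for 18 does not reproduce and exceeds those stated for 12 and 6. That is a separate error, but it sits in the same sentence. All four figures concern response; none concerns an adverse event.

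**Step 2: upper limit for an event that is not seen.** With 0 events in n patients, the exact two-sided 95% (Clopper–Pearson) upper limit is 1 − 0.025^(1/n).

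- n = 24: 1 − 0.025^(1/24) = 14.2%
- n = 18: 1 − 0.025^(1/18) = 18.5%
- n = 12: 1 − 0.025^(1/12) = 26.5%
- n = 6: 1 − 0.025^(1/6) = 45.9%
- n = 0: not estimable

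**Step 3: chance of seeing no case.** For a true event rate q this is (1 − q)^n.

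| n | q = 5% | q = 10% | q = 20% |
|---|---|---|---|
| 24 | 29% | 8% | 0.5% |
| 18 | 40% | 15% | 2% |
| 12 | 54% | 28% | 7% |
| 6 | 74% | 53% | 26% |
| 0 | 100% | 100% | 100% |

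**Step 4: the accepted extreme.** At 24 MF and 0 AMKL, the MF group has the first row of each table. The AMKL group has no data, and no analysis method can supply an estimate.

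**The case against.** The open split was a deliberate choice. Appendix IV (Amendment 7) gives the reason: more MF than AMKL patients are available. This is a small pilot in rare diseases, and 10.1.2 calls the protocol purely descriptive, so no power calculation is owed. Individual signals are covered by other means: monitoring for differentiation syndrome (4.4.4), SAE reporting within 24 hours and DMC review (7.3.3.1), and a late-toxicity visit (4.7). Adverse events are already recorded per population, so anyone with the counts could compute a bound.

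Most of this stands. It defends the enrolment rule and the absence of a power calculation, and neither is challenged here. It does not explain why the objective stayed unconditional when the split was opened. Nor does it explain why a descriptive plan gives exact intervals to the secondary endpoint and none to the primary. Recording by population is not the same as a stated analysis by population.

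Three stronger readings are tempting but not supported:

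- A reader might infer that the whole primary question could go unanswered. At 24 to 0 only the AMKL half does.
- A reader might take differentiation syndrome to be the central, rare unknown. Section 1.6 gives it weight but also cites disturbed hematopoiesis, 4.4.4 calls it theoretical, and no section gives a rate. At 5%, an event would be missed 29% of the time even in 24 patients, so a low detection chance is not due to the split alone.
- A reader might want a fixed minimum of 6 AMKL patients for any conclusion. In 10.2 that number only illustrates response precision. The upper limit is 45.9% at 6 and 1 − 0.025^(1/5) = 52.2% at 5, so there is no natural threshold there.

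**Conclusion.** The point holds as a mismatch between objective and enrolment rule, together with missing precision for the primary endpoint. Run as written, the trial can end with no AMKL safety data while AMKL safety remains in its primary objective. If some AMKL patients do enrol, an unseen event is bounded only at 45.9% with 6 patients and 26.5% with 12, and the planned analysis would not show this.

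The upper limits need no assumption beyond independent patients with a common event rate within each disease. The detection probabilities rest on assumed event rates and are illustrative only. The importance is moderate: the open split may remain, and the remedy is in the wording and the analysis plan.

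**What to change.** - **10.1.1:** report adverse event percentages separately for MF and AMKL. Give exact 95% intervals, by the method already in 10.1.2, for related events of Grade 3 or higher, SAEs, events leading to discontinuation, and differentiation syndrome.
- **10.2:** add the upper limits for an unseen event (14.2%, 18.5%, 26.5% and 45.9% for 24, 18, 12 and 6 patients; not estimable for none). Give any detection probability over a range of assumed rates and label it illustrative. Correct the standard error for 18 patients at the same time, here and in the Study Summary.
- **Study Summary, 1.6, 2.1 and 6.1:** state that AMKL safety will be described to the extent that AMKL patients accrue, with individual listings and the exact interval. Add that no conclusion on AMKL safety will be drawn from MF data, or if no AMKL patient is treated. All four places need the same wording. No fixed cut-off is needed.

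This adds no patients, visits or accrual time and keeps the flexible split. The costs are a protocol amendment with the reviews listed under 11.2 (Amendments), and a stated AMKL objective that promises less than it does now.

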10.1.2 Secondary Endpoint

To determine preliminary efficacy, response (defined as having at least PR in evaluable patients) will be reported as a proportion and 95% confidence interval using exact binomial methods. Given that this is a purely descriptive protocol, there is no set hypothesis regarding the response rate. Proportions for clinical response (defined as having at least PR or stable disease) will also be calculated. Please refer to appendices for detailed explanations of the clinical response criteria for each population.

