
Study summary and Section 10. 2 (Statistics)
	
Approximate standard errors for the estimated response rate when the true response rate is 10% are +/- 6% with a sample of 24 patients total, and +/- 9% with a sample of 12 patients in each disease group.
 
Approximately 4 potentially eligible patients are seen per month at both sites
 
DLT language within the statistics section
	
Approximate standard errors for the estimated response rate when the true response rate is 10% are +/- 6% with a sample of 24 patients total, +/- 18% with a sample of 18 patients, +/- 9% with 12 patients and +/- 10% to 12% with 6 patients.
 
Both sites corrected to read 'all sites'
 
Removed DLT language
	
Updated statistics to align with modification to disease allocation of patients.
 
Correction of typographical error(since there are more than 2 sites).
 
Correction of error, since there are no DLTs in this study.

Amendment 8 March 17, 2017			
Section(s) Affected	Prior Version	Amendment 8 Changes	Rationale

Section 4.2 Treatment administration
 
Section 5.1 Schedule of events for MF patients
	
Description of treatment administration
 
Footnote m: statement that lab and exams will be done only on day 1 of Cycle 7 and beyond.
	
Language modified: to state that beyond cycle 6, for MF patients who are stable, they will be asked to come to clinic on D1 of every even cycle and they will be given drug supply for 2 cycles to facilitate this. During these visits, labs and exams will be done as indicated in the schedule. During the odd numbered cycles, outside lab tests (only CBC and CMP) will be ordered. Patients can start their treatment at home only after the treating physician has reviewed the laboratory results and determined that they are able to continue treatment. For these cycles, the study coordinator will contact the patient on/prior to Day 1 to inform them if they can or cannot start the new cycle, and also check compliance regarding study drug intake.
 
A 'D1' added under the Cycle 7+ column
	
To facilitate patient treatment convenience and flexibility.

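### The standard error given for 18 patients (18%) is wrong: at the stated 10% response rate it is 7%, and the entry for 6 patients should be the single value 12%

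*Combined protocol and SAP*

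**What the plan says.** Section 10.2 gives the plan's only statement of precision for the response rate. It is introduced by "Approximate standard errors for the estimated response rate when the true response rate is 10" per cent, and lists "6% with a sample of 24 patients total", then "18% with a sample of 18 patients, +/- 9% with 12 patients and +/- 10% to 12% with 6 patients", each figure written as plus or minus. The Statistical Methodology row of the Study Summary carries the same sentence with the same figures. Neither place names a second response rate or a different formula for any entry.

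Section 10.1.2 defines response as at least a partial response in evaluable patients, reported as a single proportion with an exact binomial 95% confidence interval. It adds: "Given that this is a purely descriptive protocol, there is no set hypothesis regarding the response rate".

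Appendix IV shows where the entries came from. Before Amendment 7 the sentence held only the figure for 24 patients "and +/- 9% with a sample of 12 patients in each disease group". Amendment 7 removed the fixed 12/12 split between MF and AMKL and added the entries for 18 and 6 patients. The reason recorded is "Updated statistics to align with modification to disease allocation of patients".

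**The concern.** At a fixed true rate, the standard error of a proportion falls as the sample grows. The value for 18 patients must therefore lie between those for 24 and 12 patients, that is, between the stated 6% and 9%. The plan puts it at 18%, above even the value for 6 patients. The list contradicts itself before any calculation is done.

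The entry for 6 patients is odd in a different way. One rate and one sample size give one standard error, so a range has no evident source.

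What is at stake is the reader's view of how much a disease group of a given size can show. Amendment 7 allows any split of the 24 patients. The entries for 18 and 6 (which add to 24) are the only ones that describe an uneven split. A reader who relies on them would think the larger group the less informative one.

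**Working it through.** **Inputs.** True response rate p = 0.10 and sample sizes n = 24, 18, 12 and 6, all from Section 10.2. Response is a single binomial proportion (Section 10.1.2).

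**Formula.** SE = sqrt(p(1 − p)/n) = sqrt(0.09/n).

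| n | Calculation | SE | Stated | Agreement |
|---|---|---|---|---|
| 24 | sqrt(0.09/24) | 6.12% | 6% | yes |
| 18 | sqrt(0.09/18) | 7.07% | 18% | no |
| 12 | sqrt(0.09/12) | 8.66% | 9% | yes |
| 6 | sqrt(0.09/6) | 12.25% | 10% to 12% | upper end only |

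The formula reproduces two of the plan's own entries, so it is evidently the one used.

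**Could 18% be right at n = 18 for some other rate?** The standard error is largest at p = 0.5: sqrt(0.25/18) = 11.79%. A value of 18% would need p(1 − p) = 18 × 0.18² = 0.583, and p(1 − p) cannot exceed 0.25. At p = 0.10, 18% corresponds to n = 0.09/0.18² = 2.8 patients.

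**Could it come from another formula at n = 18?**
- Denominator n − 1: 7.28%.
- Agresti-type adjustment: 8.06%.
- Continuity correction: 9.85%.
- 90% half-width: 1.645 × 7.07% = 11.63%.
- 95% half-width: 1.96 × 7.07% = 13.86%.
- Half-width of the exact 95% interval: 13.6% with 1 responder, 16.7% with 2, 18.9% with 3.

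None gives 18%. A half-width reading would also spoil the entries that are correct: the 95% half-width is 12.0% at n = 24 and 17.0% at n = 12, against a stated 6% and 9%.

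**The lower end at n = 6.** A standard error of 10% at n = 6 needs p(1 − p) = 6 × 0.10² = 0.06, so p = 6.4%. At p = 0.10 it needs n = 0.09/0.10² = 9 patients. Neither is what the sentence states.

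**Size of the error at n = 18.** 18/7.07 = 2.5.

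**The case against.** The strongest reply is that nothing depends on the sentence. The primary endpoint is safety. Response is secondary and descriptive, the planned intervals are exact and computed from observed data, and Section 10.2 supports 24 patients by disease rarity and accrual rather than by precision. The figure for the full sample of 24 is correct. All of this stands and holds the point to a minor one.

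A second reply is that the figures are called approximate, and that the range for 6 patients contains the right rounded value, 12%, at its upper end. That is fair. The range is loose wording, not an impossible value, and should not be ranked with the n = 18 entry. The two faults also run in opposite directions: 18% overstates the uncertainty for 18 patients, while 10% understates it for 6.

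A third is that exact half-widths come close to 18%: 16.7% with 2 responders and 18.9% with 3. They are not standard errors, however, and no responder count at n = 18 near a 10% rate gives 18%.

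Finally, the documents do not show whether 18% is a slip in calculation or in typing, for example the sample size repeated. The cause is open, but the correction is the same. The figure appears in Section 10.2, in the Study Summary and in the Amendment 7 entry of Appendix IV, so a fault in the text extraction is very unlikely.

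**Conclusion.** The point holds, as a minor one. For 18 patients the stated standard error of 18% should be 7% (7.1%); the stated value is 2.5 times too large and exceeds the 11.8% maximum for any response rate. For 6 patients the entry should be the single value 12% (12.2%). The entries for 24 and 12 patients are correct.

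This rests on the stated true rate of 10% and on the ordinary binomial standard error. The impossibility of 18% at n = 18 does not depend on the rate. No design feature, test, decision rule or planned analysis changes.

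**What to change.** In Section 10.2 and in the Statistical Methodology row of the Study Summary, keep the opening of the sentence and its 10% rate, and replace the list with: 6% with 24 patients in total, 7% with 18, 9% with 12 and 12% with 6.

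The cost is one sentence in two places, with a line in the history of changes. Design, conduct and analysis are untouched.

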11.0 STUDY MANAGEMENT

11.1 Institutional Review Board (IRB) Approval and Consent

It is expected that the IRB will have the proper representation and function in accordance with federally mandated regulations. The IRB should approve the consent form and protocol.

In obtaining and documenting informed consent, the investigator should comply with the applicable regulatory requirement(s), and should adhere to Good Clinical Practice (GCP) and to ethical principles that have their origin in the Declaration of Helsinki.

Before recruitment and enrollment onto this study, the patient will be given a full explanation of the study and will be given the opportunity to review the consent form. Each consent form must include all the relevant elements currently required by the FDA Regulations and local or state regulations. Once this essential information has been provided to the patient and the investigator is assured that the patient understands the implications of participating in the study, the patient will be asked to give consent to participate in the study by signing an IRB approved consent form.

Prior to a patient's participation in the trial, the written informed consent form should be signed and personally dated by the patient and by the person who conducted the informed consent discussion.

11.2 Amendments

The Principal Investigator will formally initiate all amendments to the protocol and/or informed consent. All amendments will be subject to the review and approval of the appropriate local, institutional, and governmental regulatory bodies, as well as by

Janssen Scientific Affairs. Amendments will be distributed by the lead institution (Northwestern) to all affiliate sites upon approval by the Northwestern University IRB.

11.2 Registration Procedures

Patients may not begin protocol treatment prior to registration. All patient registrations will be registered centrally through the Clinical Research Office at Northwestern University before enrollment to study. Please contact the assigned Quality Assurance Monitor (QAM) or email the QA Department ([contact]) for questions regarding patient registration. For all potential patients, study teams are asked to inform the QAM of the date and time that the patient will need to be registered.

Prior to registration, eligibility criteria must be confirmed by the assigned QAM. The study coordinator will screen all subjects for potential registration via the web-based application NOTIS (Northwestern Oncology Trial Information System), which is available at: <https://notis.nubic.northwestern.edu>. Please note that a username and password is required to use this program, and will be provided during site activation prior to training on the NOTIS system.

BEFORE a patient can be treated on study, please complete and submit the following items to confirm eligibility and receive an identification number:

- Patient's signed and dated informed consent form (upload to NOTIS and keep original hard copy in a secure location/study chart)
- Eligibility checklist (signed and dated by the treating physician – upload to NOTIS)
- Eligibility eCRF (complete in NOTIS)
- Copy of the pathology report (upload to NOTIS)

The QAM will review all source documentation required to confirm eligibility that is readily available in the patient's electronic medical record (EMR). Any information that is not available in the EMR must be de-identified and emailed to the QAM. Once the QAM confirms the patient is eligible, he or she will register the patient, assign a subject identification number, provide a cohort assignment, and send a confirmation of registration to involved personnel. Registration will then be complete and the patient may begin study treatment.

11.3 Instructions for Participating Sites

Before the study can be initiated at any site, the following documentation must be provided to the Clinical Research Office at Northwestern University:

- Signed and completed Letter of Invitation to participate in the study.
- Signed copy of Northwestern University's Data Monitoring Committee policy pertaining to data submission.
- Draft informed consent form should for review/approval prior to submission to the local IRB
- A copy of the official IRB approval letter for the protocol and informed consent.
- CVs and medical licensure for the local PI and any sub-investigators who will be involved in the study at the site.
- Form FDA 1572 appropriately filled out and signed with appropriate documentation.

Additional activities may be required prior to site activation (i.e. contract execution, study-specific training). Full requirements will be outlined in a memo upon receipt of the signed Letter of Invitation.

11.4 Data Submission and Monitoring/Auditing

Once a subject is confirmed and registered to the study, eCRFs should be submitted through NOTIS according to the detailed data submission guidelines (will be provided in a

separate document). Generally, all data during the first cycle must be submitted on a weekly basis. Thereafter data will be due at the end of each cycle.

This study will be conducted in compliance with the Data Safety Monitoring Plan (DSMP) of the Robert H. Lurie Comprehensive Cancer Center of Northwestern University (please refer to Appendices for additional information). The level of risk attributed to this study requires high intensity monitoring, as outlined in the DSMP. The assigned QAM, with oversight from the Data Monitoring Committee, will monitor this study in accordance with the study phase and risk level.

